3.5 Appendix 5: Contraceptive Guidance and Collection of Pregnancy Information

3.5.1 Definitions

Woman of childbearing potential

A woman is considered fertile following menarche and until becoming post-menopausal unless permanently sterile (see below).

If fertility is unclear (eg, amenorrhea in adolescents or athletes) and a menstrual cycle cannot be confirmed before first dose of study intervention, additional evaluation should be considered.

Women in the following categories are not considered women of childbearing potential

- a. Premenarchal
- b. Premenopausal female with 1 of the following:
 - Documented hysterectomy
 - Documented bilateral salpingectomy
 - Documented bilateral oophorectomy

For individuals with permanent infertility due to an alternate medical cause other than the above, (eg, Mullerian agenesis, androgen insensitivity), Investigator discretion should be applied to determining study entry.

Note: Documentation can come from the site personnel's: review of the participant's medical records, medical examination, or medical history interview.

Females on HRT and whose menopausal status is in doubt will be required to use one of the non-estrogen hormonal highly effective contraception methods if they wish to continue their HRT during the study. Otherwise, they must discontinue HRT to allow confirmation of postmenopausal status before study enrollment.

3.5.2 Contraception Guidance

Female participants of childbearing potential must use a highly effective method of contraception, as shown in the table below. Male participants must agree to use condoms. This applies from the time of ICF signature until the end of the study period.

Table 5 Highly Effective Contraception Methods

-
- Implantable hormonal contraception associated with inhibition of ovulation
 - Intrauterine device
 - Intrauterine hormone-releasing system
 - Bilateral tubal occlusion
 - Hormonal contraception with inhibition of ovulation, either estrogen and progestogen containing or progesterone-only
 - Vasectomized partner if sole sexual partner
 - Sexual abstinence
-

Modified from: Clinical Trial Facilitation Group 2014: Recommendations related to contraception and pregnancy testing in clinical trials (CTFG 2014).

3.5.3 *Collection of Pregnancy Information*

Male participants with partners who become pregnant

- The Investigator will attempt to collect pregnancy information on any male participant's female partner who becomes pregnant while the male participant is in this study. This applies only to male participants who receive study intervention.
- After obtaining the necessary signed informed consent from the pregnant female partner directly, the Investigator will record pregnancy information on the appropriate form and submit it to the Sponsor within 24 hours of learning of the partner's pregnancy. The female partner will also be followed to determine the outcome of the pregnancy. Information on the status of the mother and child will be forwarded to the Sponsor. Generally, the follow-up will be no longer than 6 to 8 weeks following the estimated delivery date. Any termination of the pregnancy will be reported regardless of fetal status (presence or absence of anomalies) or indication for the procedure.

Female participants who become pregnant

- The Investigator will collect pregnancy information on any female participant who becomes pregnant while participating in this study. The initial information will be recorded on the appropriate form and submitted to the Sponsor within 24 hours of learning of a participant's pregnancy.
- The participant will be followed to determine the outcome of the pregnancy. The Investigator will collect follow-up information on the participant and the neonate and the information will be forwarded to the Sponsor. Generally, follow-up will not be required for longer than 6 to 8 weeks beyond the estimated delivery date. Any termination of

pregnancy will be reported, regardless of fetal status (presence or absence of anomalies) or indication for the procedure.

- While pregnancy itself is not considered to be an AE or SAE, any pregnancy complication or elective termination of a pregnancy for medical reasons will be reported as an AE or SAE.
- A spontaneous abortion (occurring at < 22 weeks gestational age) or still birth (occurring at > 22 weeks gestational age) is always considered to be an SAE and will be reported as such.
- Any post-study pregnancy related SAE considered reasonably related to the study intervention by the Investigator will be reported to the Sponsor as described in [Appendix 4](#). While the Investigator is not obligated to actively seek this information in former study participants, he or she may learn of an SAE through spontaneous reporting.
- Any female participant who becomes pregnant while participating in the study will discontinue study intervention.

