	
Screening/Randomization) who are lactating, or who are pregnant as determined by a positive serum pregnancy test at Visit 1 – Screening/Randomization. Women of childbearing potential must agree to use acceptable methods of birth control throughout the study.
 
a. Women who are breastfeeding or who have a positive serum hCG/urine pregnancy test at the screening or Baseline (BL) Visit
 
28. Females and males of childbearing potential unwilling or unable to utilize the following acceptable methods of birth control: tubal ligation, transdermal patch, intrauterine devices/systems, oral/implantable/injectable or contraceptives, diaphragm or cervical cap with spermicide, or vasectomized partner for females; condoms with spermicidal agent and vasectomy for males; or sexual abstinence for males and females
 
29. Participation in any other investigational device or drug clinical research study within 12 weeks of Visit 1 – Screening/ Randomization and during the duration of enrollment
 
30. Contraindication to the study medications or fluorescein dye
 
31. Other ocular pathologies that, in the investigator’s opinion, would interfere with the participant’s vision in the study eye
 
32. Ocular media of insufficient quality to obtain fundus photographs, fluorescein angiography, and OCT images in the study eye
 
33. Concomitant use of Semaglutide (Wegovy®, Ozempic®, Rybelsus®), Thiazolidinediones (Actos®, Avandia®), Liraglutides (Victoza®, Saxenda®), Dulaglutide (Trulicity®), or Tirzepatide (Mounjaro®) within 12 months prior to Visit 1 (allowed if a stable dose has been established for at least 1 year of use)
 
a. Plans to start concomitant use of Semaglutides, Thiazolidinediones, Liraglutides, Dulaglutides, or Tirzepatides during the study duration is exclusionary

--	---

Note: The inclusion and exclusion criteria apply through study duration for non-emergency ocular procedures and surgery.	
Duration of Treatment:	24 weeks

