17. Concomitant use of any topical ophthalmic medications in the study eye, including dry eye or glaucoma medications, unless on a stable dose for at least 90 days prior to study enrollment and expected to stay on stable dose throughout study participation. Topical eyedrops are allowed but not within ± 10 minutes of study drop application
18. Contact lens use from time of screening throughout the study
19. Central corneal changes from dry eye that are visually significant and/or Sjogren's syndrome
20. Visually significant Fuchs endothelial dystrophy or other diagnosed conditions of corneal compromise including Anterior Basement Membrane Dystrophy, or any corneal dystrophy affecting central vision (peripheral processes are not exclusionary)
21. Chronic or recurrent uveitis in the study eye
22. Ongoing ocular infection or inflammation in either eye
23. A history of cataract surgery complicated by vitreous loss in the study eye
24. Congenital eye malformations in the study eye
25. A history of penetrating ocular trauma in the study eye
26. Cognitive impairment that, in the opinion of the investigator, could compromise compliance with the requirements of the study
27. Females of childbearing potential (ie, who are not postmenopausal for at least 1 year or surgically sterile for at least 6 weeks prior to Visit 1 – Screening/Randomization) who are lactating, or who are pregnant as determined by a positive serum pregnancy test at Visit 1 – Screening/Randomization. Women of childbearing potential must agree to use acceptable methods of birth control throughout the study
 - a. Women who are breastfeeding or who have a positive serum hCG/urine pregnancy test at the screening or BL Visit
28. Females and males of childbearing potential unwilling or unable to utilize the following acceptable methods of birth control: tubal ligation, transdermal patch, intrauterine devices/systems, oral/implantable/injectable or contraceptives, diaphragm or cervical cap with spermicide, or vasectomized partner for females; condoms with spermicidal agent and vasectomy for males; or sexual abstinence for males and females
29. Participation in any other investigational device or drug clinical research study within 12 weeks of Visit 1 – Screening/Randomization and during the duration of enrollment
30. Contraindication to the study medications or fluorescein dye
31. Other ocular pathologies that, in the investigator's opinion, would interfere with the participant's vision in the study eye

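### Exclusions 27 and 28 accept contraception for women that section 3.5.2 and Table 5 do not, so a woman relying on a diaphragm or cap can be randomized without meeting the protocol's own rule

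*Protocol*

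**What the plan says.** **The conduct rule.** Protocol section 3.5.2 (Appendix 5) reads: "Female participants of childbearing potential must use a highly effective method of contraception, as shown in the table below". On timing it adds: "This applies from the time of ICF signature until the end of the study period". Table 5 has seven entries: ovulation-inhibiting implants, intrauterine devices, hormone-releasing intrauterine systems, bilateral tubal occlusion, other ovulation-inhibiting hormonal methods, a vasectomized partner under a condition, and abstinence. For men, section 3.5.2 asks for condoms and nothing else.

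**The entry rule.** Exclusion 27 says: "Women of childbearing potential must agree to use acceptable methods of birth control throughout the study". It names no methods. Exclusion 28 excludes people who will not or cannot use a listed method, and for women it lists "tubal ligation, transdermal patch, intrauterine devices/systems, oral/implantable/injectable or contraceptives, diaphragm or cervical cap with spermicide, or vasectomized partner for females". For men, and for abstinence in both sexes, it continues: "condoms with spermicidal agent and vasectomy for males; or sexual abstinence for males and females". Both exclusions carry this wording in the synopsis and in section 2.9.

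Neither exclusion refers to Appendix 5 or Table 5, and neither uses the highly effective standard. The SAP does not deal with contraception.

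**The concern.** Eligibility is decided on the inclusion and exclusion criteria, which the schedule of activities places at screening and baseline. Exclusion 28 is a specific list of methods introduced as the acceptable ones, so a site has good reason to treat it as complete. If that list is wider than Table 5, a site can apply the criteria exactly and still randomize a woman who is out of line with section 3.5.2 from the day she signs consent.

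What is at stake is exposure of a pregnancy to an investigational drug. The protocol treats this as serious: pregnancy is one of the listed reasons for mandatory withdrawal from study intervention (section 2.14.10.1), and pregnancies are followed to outcome (sections 2.18.5 and 3.5.3).

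**Working it through.** No arithmetic applies. The check compares the methods exclusion 28 allows women with the entries of Table 5. All the text compared is current version 5.0 text, not amendment history.

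| Method in exclusion 28 (women) | Table 5 | Result |
|---|---|---|
| Tubal ligation | Bilateral tubal occlusion | Matches, reading the two terms as the same |
| Intrauterine devices/systems | Device and hormone-releasing system, listed separately | Matches |
| Abstinence | Listed | Matches |
| Implant | "Implantable hormonal contraception associated with inhibition of ovulation" | Condition absent from exclusion 28 |
| Patch, oral, injectable | "Hormonal contraception with inhibition of ovulation, either estrogen and progestogen containing or progesterone-only" | Condition absent from exclusion 28 |
| Vasectomized partner | "Vasectomized partner if sole sexual partner" | Condition absent from exclusion 28 |
| Diaphragm or cervical cap with spermicide | Not listed | Conflict |

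Step by step, for a woman whose only method is a diaphragm with spermicide:

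1. Exclusion 27: she agrees to use an acceptable method. Exclusion 28 names hers as acceptable, so she is not excluded.
2. Exclusion 28: she is willing and able to use a listed method, so she is not excluded.
3. Inclusion 5 asks for willingness to attend visits and comply with study procedures. It does not mention contraception, so it does not direct the site to Table 5.
4. Section 3.5.2: her method is not in Table 5, so she does not meet it.

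The same four steps apply to the cervical cap. This is the one clear conflict for women.

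The missing conditions are weaker evidence. A vasectomized partner fails Table 5 only if he is not the sole partner. A hormonal method fails only if the product does not inhibit ovulation, and the documents identify no such product.

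For men the differences run both ways. Exclusion 28 adds spermicide and vasectomy to condoms, without saying whether both are needed or either will do; section 3.5.2 mentions neither. Exclusion 28 accepts abstinence; section 3.5.2 asks men for condoms without exception.

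**The case against.** **The stricter rule already governs.** Section 3.5.2 is mandatory from consent, and a woman using, say, an intrauterine device satisfies both texts. This stands. A reader might infer that the protocol holds two rival rules with nothing to choose between them. The documents do not support that for women: section 3.5.2 binds every woman of childbearing potential, and the exclusions do not release her from it. What remains is that the point at which the site decides on entry does not apply the rule.

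**Appendix 5 is only guidance.** The section title says so, but its text is an obligation.

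**Pregnancy testing covers the risk.** A negative serum test is required before randomization, a negative urine test is required before treatment continues at each visit, and drug stops at once on a positive test (section 2.17.4 and the schedule footnotes). This limits exposure. It detects a pregnancy rather than preventing one, so some risk remains.

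**The hormonal and sole-partner differences are loose drafting.** This largely stands. The hormonal phrase in exclusion 28 is garbled and may have lost a word. A reader might infer a deliberate waiver of Table 5's conditions, or might count methods to show a wide gap. Neither is supported: nothing shows intent, and any count depends on how the entries joined by slashes are split.

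**Enrolment may be over.** SAP section 4.2 describes enrolment and randomization in the past tense. If recruitment has closed, changing the entry criteria achieves little. Enrolled women still come under section 3.5.2.

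**Conclusion.** The point holds as a mismatch within the protocol. The eligibility criteria accept two barrier methods that the protocol's mandatory contraception rule does not, and they word two further conditions more loosely. A woman relying on a diaphragm or cap can be randomized without meeting section 3.5.2.

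Its size is modest. The documents give no number of women of childbearing potential or of users of these methods, so the number affected cannot be stated; it could be zero. The issue concerns participant safety and consistent eligibility, with no effect on the efficacy analysis, sample size or power. Fixing it is desirable rather than essential.

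The conclusion assumes that sites treat exclusion 28 as the working list, and that no eligibility checklist or consent form already imposes Table 5. Those documents were not available to check.

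The male wording is a secondary point. Neither male text is stricter throughout, so the documents do not show which rule the sponsor intended.

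**What to change.** 1. **Exclusion 28, synopsis and section 2.9.** Replace the female method list with: *Women of childbearing potential who are unwilling or unable to use a method listed in Table 5 (section 3.5.2), in use by randomization and continued to the end of the study.*
2. **Exclusion 27, both places.** Replace the acceptability standard with the same reference: *a method listed in Table 5 (section 3.5.2), in use by randomization and continued to the end of the study.*
3. **Leave the consent-signature start date in section 3.5.2 only.** As an entry test it could exclude a woman who moves to a Table 5 method during the screening window (Day -21 to -1).
4. **Women already enrolled.** Counsel anyone whose method is outside Table 5 to change to one that is in it. Section 3.5.2 already requires this, so it need not wait for an amendment.
5. **Men.** The sponsor should choose one rule and state it identically in exclusion 28 (both places) and section 3.5.2: whether spermicide is needed, whether vasectomy adds to condoms or replaces them, and whether abstinence suffices.

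The cost is a protocol amendment with IRB/IEC approval, health authority approval if the change is substantial (section 3.1.1), and a matching eligibility checklist. If the consent form changes, participants still in the study must be re-consented (section 3.1.3). Visits, data collection and analyses stay as they are. If enrolment has closed, items 1 and 2 add little, and items 4 and 5 carry the remaining benefit.

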**REVISION HISTORY**

| Version No. | Effective Date | Summary of Change(s)   |
|-------------|----------------|--|
| 1.0         | 12-May-2022    | New document   |
| 2.0         | 30-June-2023   | All the changes made in this version are described in Appendix 6.3 |
| 3.0         | TBD            | All the changes made in this version are described in Appendix 6.3 |

**LIST OF ABBREVIATIONS**

| Abbreviation/Acronym | Definition/Expansion                 |
|-----------------------------|---|
| AE                          | Adverse Event                               |
| AESI                        | Adverse Event of Special Interest           |
| ANCOVA                      | Analysis of Covariance                      |
| Anti-VEGF                   | Anti-Vascular Endothelial Growth Factor     |
| ASNV                        | Anterior Segment Neovascularization         |
| ATC                         | Anatomical Therapeutic Chemical             |
| AUC                         | Area Under the Curve                        |
| BCVA                        | Best Corrected Visual Acuity                |
| BID                         | Twice Daily                                 |
| BL                          | Baseline                                    |
| BMI                         | Body Mass Index                             |
| CFP                         | Color fundus photography                    |
| CI                          | Confidence interval                         |
| CI-DME                      | Center-Involved Diabetic Macular Edema      |
| CNV                         | Choroidal Neovascularization                |
| CSR                         | Clinical Study Report                       |
| CST                         | Central Subfield Thickness                  |
| DME                         | Diabetic Macular Edema                      |
| DR                          | Diabetic Retinopathy                        |
| DRIL                        | Disorganization of Retinal Inner Layers     |
| DRSS                        | Diabetic Retinopathy Severity Scale         |
| eCRF                        | Electronic Case Report Form                 |
| EOS                         | End of Study                                |
| EOT                         | End of Treatment                            |
| ETDRS                       | Early Treatment Diabetic Retinopathy Study  |
| ETRDR                       | Early Treatment Report Diabetic Retinopathy |
| FA                          | Fluorescein Angiography                     |
| FAS                         | Full analysis set                           |
| FAZ                         | Foveal Avascular Zone                       |

| Abbreviation/Acronym | Definition/Expansion                  |
|-----------------------------|--|
| HbA1c                       | Glycosylated Hemoglobin                      |
| ICH                         | International Conference on Harmonisation    |
| ICE                         | Intercurrent Event                           |
| IOP                         | Intraocular Pressure                         |
| IRMA                        | Intraretinal microvascular abnormality       |
| ITT                         | Intent-to-Treat                              |
| IVT                         | Intravitreal Injection                       |
| MAR                         | Missing at random                            |
| MedDRA                      | Medical Dictionary for Regulatory Activities |
| MH                          | Mantel-Haenszel                              |
| MV                          | Macular Volume                               |
| nAMD                        | Neovascular Age-Related Macular Degeneration |
| NPDR                        | Non-Proliferative Diabetic Retinopathy       |
| OCT                         | Optical Coherence Tomography                 |
| OCTA                        | Optical Coherence Tomography – Angiography   |
| OU                          | Both eyes                                    |
| PDR                         | Proliferative Diabetic Retinopathy           |
| PPS                         | Per-Protocol Set                             |
| PRP                         | Pan-retinal Photocoagulation                 |
| PT                          | Preferred Term                               |
| QID                         | Four Times Daily                             |
| SAE                         | Serious Adverse Event                        |
| SAP                         | Statistical Analysis Plan                    |
| SD                          | Standard deviation                           |
| SD-OCT                      | Spectral-Domain Optical Coherence Tomography |
| SE                          | Standard error                               |
| SE                          | Study eye                                    |
| SI                          | Standard International                       |
| SoA                         | Schedule of Activities                       |
| SOC                         | System Organ Class                           |
| TEAE                        | Treatment-Emergent Adverse Event             |

# Parexel International

OcuTerra Therapeutics, Inc.  
OTT166-201

Statistical Analysis Plan

| Abbreviation/Acronym | Definition/Expansion              |
|-----------------------------|--|
| TESAE                       | Treatment Emergent Serious Adverse Event |
| VEGF                        | Vascular Endothelial Growth Factor       |
| VTC                         | Visually Threatening Complications       |

**1 INTRODUCTION**

OTT166 is a representative from a new class of drugs, i.e., a topical integrin inhibitor targeted to the back of the eye. It is being developed for treatment of Diabetic Retinopathy (DR). This study is designed to provide the proof of concept that non-proliferative diabetic retinopathy (NPDR) and mild proliferative diabetic retinopathy (PDR) can be effectively treated with a topical eye drop formulation of OTT166. Furthermore, this study is designed to determine the dose-exposure response of OTT166 in terms of efficacy and safety in order to support the dose selection for the subsequent pivotal Phase 3 studies with OTT166 in DR.

This Statistical Analysis Plan (SAP) describes all planned analyses for the Clinical Study Report (CSR) of Phase 2 Randomized, Double-Masked, Vehicle-Controlled, Multicenter Study to Evaluate the Safety and Efficacy of OTT166 Ophthalmic Solution in the Treatment of DR.

The structure and content of the SAP are based upon the International Conference on Harmonisation (ICH) E3 – Guideline for Industry Structure and Content of Clinical Study Reports.

The content of this SAP is based on following study document:

- Study Protocol Version 5.0 dated October 10, 2023.

